Recent studies using a novel QA/QC tool (LaraTM System) for the radiotracer injection process revealed that current means to detect infiltration do not completely identify all infiltrations/obstructions [7]. Since infiltrations may not be visible in the standard field of view (FOV) and since the impact of a peripheral circulatory obstruction may not be visible even if an injection site is in the FOV, it is possible for reading and treating physicians to be unaware that a patient's image and quantification has been impacted. Additionally, when current means do detect an infiltration, they under-represent the severity because they are not capturing that infiltrations often resolve during the uptake period. As a result, infiltrations or obstructions may cause SUV inaccuracy and could adversely impact staging and tumor assessments.

The FDA-listed Lucerno Dynamics LaraTM System is comprised of sensors, a reader and software. The sensors are connected to a reader that provides temporary data storage. By using similar principles as PET scanning technology (i.e., scintillating crystal and photomultiplier), the sensors measure the presence of radiolabeled tracer in target areas of interest. The system software that has been developed uses time activity curves (TACs) to provide a way to determine whether radiolabeled tracers commonly used in PET/CT remain pooled near the injection site during the uptake period, rather

than circulating in the vascular system. Past and ongoing studies using standard PET/CT and dynamic images have confirmed the Lara™ System is a better tool than current imaging to identify and characterize the presence of radiotracer near the injection site during uptake. Because the Lara™ sensor is located near the injection site, it captures all infiltrations and obstructions and is agnostic to imaging FOV. With a one second frame rate, Lara™ dynamically captures radiotracer presence during the entire uptake period, and therefore better characterizes infiltrations as compared to static images taken at 60 minutes post injection. Lara's TAC feedback on the fidelity of an FDG injection of the entire uptake period could help reduce erroneous infiltration interpretations.

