3.4.2 Exclusion criteria

- Subjects unwilling or unable to tolerate a repeat PET/CT scan.
- Subjects with meaningful medical intervention between PET/CT scans that would likely impact SUV.
- Subjects with follow-up moderate or greater infiltrations as determined by the PI and Lara score.
- Patients for whom an infiltration score cannot be determined, such as when ports or other central lines are used.

- Pregnant women.
- Subjects who are not able to read/understand English

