3.5 Study procedure

The LaraTM System is currently commercially available and is being used on site as part of a Quality Improvement project on all patients undergoing PET/CT studies. The LaraTM System will continue to be used on all patients undergoing PET/CT scans at the completion of the Quality Improvement Study to provide ongoing quality control and quality assurance of the injection process. Patients whose scans are determined by the Nuclear Medicine physician, or their designee, to have a moderate or greater infiltration based on review of the standard PET images and/or LaraTM TACs will be asked to return for a repeat PET/CT scan within 1-7 calendar days. In the event that the follow up scan shows any infiltration; the Nuclear Medicine physician or designee will be consulted to determine appropriate next steps. Site will duplicate the PET/CT protocol of the initial scan as carefully as possible for the follow up scan. Factors that will help ensure consistency of scan conditions to be recorded on the Case Report Form (CRF) (Appendix 1) include (but are not limited to):

- Same pre-procedure process and instructions to subject
- Time of day
- Glucose
- Time from injection to scanning
- PET/CT bed protocol
- Fasting and pre-scan activity level
- Subject weight
- BMI
- Prescribed FDG dose
- Flush volume
- Concomitant medications
- Any other data deemed pertinent by the technologist and/or Nuclear Medicine physician

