3.6.4 Data Analysis

Upon the determination of an infiltrated subject, the technical staff will notify the Nuclear Medicine physician to determine the severity and appropriateness of the subject for the study. To qualify for the study, the subject will need:

- at least one target lesion; and

- at least a moderate infiltration as determined by visual analysis and/or infiltration score from the Lucerno Dynamics' Lara™ system software

Data will be analyzed on each individual subject after the second imaging session. The scans will be presented in tandem such that simultaneous measurements may be performed using a qualified image analysis program, such as MIM version 6.5. Up to five target lesions will be assessed, chosen to include the target lesion or lesions defined under the PERCIST criteria [8]. For each lesion, SUV peak will be measured, and a volume contour will be created using mean liver SUV+2SD as a threshold., SUVmean, metabolic tumor volume, and total lesion glycolysis will be measured from the contour. The lesions chosen will be the same for each scan, however differences in the scans may affect the volume contour. Liver and blood pool measurements will also be made as for PERCIST criteria.

SUV will be descriptively compared for the original and re-test. Our expectation is that SUV will increase at the re-test, although we are not amply powered to conduct a rigorous statistical test. We will also evaluate the relationship between SUV values and the Lara score by computing a Pearson's correlation coefficient. We hypothesize this correlation will be positive.

We hypothesize that presence of venous stasis (a cessation or impairment of venous flow) may have an influence on the relationship on SUV scores. We will conduct a sensitivity analysis by conducting analyses with and without stasis cases. Specifically, we will compare the % change in SUV values between test and re-test and the correlation coefficient of % SUV change and Lara score in the samples including and excluding stasis cases.

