To assess the exploratory objective of whether extravasation of radiotracer could influence initial staging, for patients where the type of primary solid tumor is known the T, N, and M stages will be assessed to the extent possible by PET/CT for each scan and an overall stage assigned. This will be done even if the scan was performed for response assessment or follow up. No additional imaging or clinical information will be used and it is recognized that this assessment may not generate the true clinical stage. However, the comparison between the two scans will still provide information regarding the risk of changing stage based on missed or mischaracterized lesions after an extravasation event. To provide more granular information, the number of FDG avid regional nodes and number of FDG avid non-nodal metastases (capped at 25 each) will also be recorded for each scan.

For the exploratory objective of whether extravasation can influence apparent response to therapy, we will use the infiltrated and repeat scans to explore the impact of infiltrations on PERCIST criteria if there is an existing PET/CT scan for

comparison. This other PET/CT scan could either be a prior or a follow-on PET/CT scan that has a Lara-validated injection.

All scans will be analyzed by a qualified Nuclear Medicine physician and reported using the study imaging charter. Any measurements made for the clinical reports will not be used for this analysis. To mitigate bias, a second blinded radiologist will independently analyze the scans.

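### Section 3.6.4 relies on a blinded second reader but describes no masking, so the blind is not secured where infiltration is visible on the images

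*Combined protocol and SAP*

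**What the plan says.** Entry. Under section 3.5 the Nuclear Medicine physician or a designee may call a "moderate or greater infiltration based on review of the standard PET images and/or LaraTM TACs". Section 3.6.4 repeats the rule: a subject needs "at least a moderate infiltration as determined by visual analysis and/or infiltration score" from the Lara software. Either source is enough, so visual review alone can qualify a patient.

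Reading. Section 3.6.4 states: "The scans will be presented in tandem such that simultaneous measurements may be performed". A Nuclear Medicine physician reads all scans and reports them under a study imaging charter. Then: "To mitigate bias, a second blinded radiologist will independently analyze the scans". The section does not define what the second reader is blinded to. It mentions no cropping of the injection site, no removal of dates or Lara data and no random ordering of the scans.

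Expectation. The same section states that SUV is expected to be higher at the re-test.

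Visibility. Section 1.0 limits the problem: "Since infiltrations may not be visible in the standard field of view". It adds that infiltrations often resolve during uptake.

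**The concern.** Removing labels and dates blinds a reader only to what is written on the image. Retained tracer at the injection site is part of the image, and it is the same sign by which a patient may have been enrolled. A reader given unmasked scans can therefore often work out which scan of the pair is the infiltrated one.

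This matters because the direction of the expected result is declared and some outcomes depend on judgment. The staging objective asks whether lesions are missed or misread after an extravasation. A reader who knows which scan is infiltrated may search the other one harder, and so find more nodes or metastases there, or a higher stage. That would produce the hypothesised pattern without any effect of infiltration on the images.

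**Working it through.** No figure in the protocol bears on this, so the check sets the passages side by side and adds one illustration.

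1. **Can the sign be on the image?** Yes. Sections 3.5 and 3.6.4 both allow diagnosis by visual review. For a patient who entered that way, the infiltration was visible on the standard images.

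2. **Does it separate the two scans?** Usually, but not always. Section 3.4.2 excludes "Subjects with follow-up moderate or greater infiltrations as determined by the PI and Lara score", so a retained pair has one qualifying infiltrated scan. Section 3.5 foresees that the follow-up scan may show some infiltration, so a lesser one can appear on the repeat scan and blur the contrast.

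3. **Is it hidden from the second reader?** Section 3.6.4 describes no such step. If the tandem display also applies to the second reader, which the section does not say explicitly, the site on one scan is seen directly beside its counterpart.

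4. **Which outcomes are open to judgment?**
   - Most open: T, N and M, overall stage, and counts of FDG-avid regional nodes and non-nodal metastases (each capped at 25). All are exploratory.
   - Partly open: lesion choice. Up to five lesions are chosen; they must include the PERCIST targets and be the same on both scans.
   - Little open: SUVpeak on a clear lesion, and the contour-based measures (SUVmean, MTV, TLG), because the contour follows a threshold of mean liver SUV + 2SD.

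5. **Illustration of size.** Let v be the share of pairs in which visible infiltration singles out one scan. The documents do not give v, so it is an assumption. If the reader guesses at 50% in the other pairs, then P(correct identification) = v + 0.5(1 − v), and out of 20 patients 20v are unblinded by the image.

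| v (assumed) | P(correct) | Unblinded of 20 |
|---|---|---|
| 0 | 50% | 0 |
| 0.25 | 62.5% | 5 |
| 0.5 | 75% | 10 |
| 0.75 | 87.5% | 15 |
| 1.0 | 100% | 20 |

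6. **Weight of one changed call.** With n patients staged, one changed stage call moves the stage-change proportion by 1/n. At the cap, 1/20 = 5 percentage points. Staging is restricted to patients whose primary solid tumor type is known, and lymphoma patients are also eligible, so n may be below 20 and the step larger. This is the weight of a single call. It does not estimate bias.

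**The case against.** The strongest reply is that the documents show silence, which is not the same as failure. A reader might infer that the second read is in fact unblinded. That does not follow: reads are reported under an imaging charter that is not in the documents and may specify masking. This stands, and the conclusion is limited accordingly.

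A reader might also infer that the blinded read is the only protection against bias. It is the only measure that section 3.6.4 labels as such, but others are stated: measurements from clinical reports are not used, the second read is independent, staging uses no other imaging or clinical information, contours follow a liver threshold, and the same lesions are read on both scans. These stand too, although none of them hides which scan was infiltrated.

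A third tempting reading is that the primary SUV result is compromised through hand-edited contours. The protocol describes a threshold contour and no manual editing, so the documents do not support this.

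Nor do they support the claim that every visually diagnosed patient is unblinded, because the repeat scan may also show activity at the injection site.

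Finally, the affected reads are exploratory, in a study that calls its analyses descriptive. That lowers the stakes. It does not remove the point, because descriptive results on stage change will still be read as evidence of the effect of infiltration.

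**Conclusion.** The protocol does not secure the blind of its second reader. Where the injection site is in view and only one scan shows the infiltration, or shows it clearly more, a reader of unmasked images can tell the scans apart. This goes beyond an undefined term, since stripping labels alone would not solve it.

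The exposure falls mainly on the exploratory staging and lesion counts, to some extent on lesion choice, and little on the primary SUV measurements. The number of patients affected cannot be derived from the documents; the range is 0 to 20. The conclusion assumes that the charter does not already require masking and that the second reader sees the scans as section 3.6.4 describes them. If the charter does require it, a cross-reference in section 3.6.4 settles the point.

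**What to change.** In section 3.6.4, or in the charter with a cross-reference, state that:

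- Before the second read, the study team crops or masks the injection site on each scan and the same region on the paired scan. If the injection side differs between scans, both arms are masked on both.
- Scan date, scan order and Lara data are removed, and the order or screen position of the scans is randomised.
- The second reader completes staging and lesion counts on each masked scan separately. The tandem display is used only afterwards, for SUV, MTV and TLG.
- Eligibility review continues to use the unmasked images.
- If a lesion lies in the masked region, both scans of that pair are unmasked, the pair is flagged as unblinded, and results are reported with and without flagged pairs.

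Optionally, the second reader records a guess of which scan was infiltrated, which would show how well the masking worked.

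The cost is a few minutes of image preparation per subject and rare flagged exceptions, with no extra scan or reader. Weaker cues, such as lower overall uptake on the infiltrated scan, will remain, so masking reduces the exposure without removing it.

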4.0 RISK ANALYSIS

Minimal risk to the patient arises from exposure to radiation from one additional PET/CT. There are no anticipated risks associated with the effort to help assure both PET/CT scans protocols are as similar as possible. It is possible that the repeat scan will reveal additional abnormalities not seen on the initial scan, which could cause psychological distress. There is a theoretical risk of disclosure of protected health information. To minimize this risk, all data collection will be performed in the Nuclear Medicine department. Limited PHI will be included in the research record, and all data will be stored on encrypted devices per health center policy. A log of study accession numbers, which could reidentify patients through the electronic medical record, coupled to study patient identifier will be maintained on an encrypted device to allow auditing of the data. The study team will comply with all site procedures and policies to protect confidentiality and minimize any risk to subject privacy.

4.1 Adverse event reporting

Serious Adverse Events will be reported and recorded with the patient data on the Adverse Event Form. Any serious adverse event, including loss of confidentiality, will be reported to the IRB per site requirements, and to the study sponsor within 24 hours of knowledge of the event. There are no experimental drugs or devices being used in this study.

4.2 Withdrawal of subjects

Any subject in the study may withdraw from the study at any time. In such cases the reason for withdrawal will be recorded and determination will be made by the site PIs as to its association with the research.

5.0 MONITORING PROCEDURES

Monitoring of the study for compliance with the clinical protocol and with FDA regulations will include at least one on-site visit by clinical staff of Lucerno. The Study PIs will permit direct access of the study monitor and appropriate regulatory authorities to the study data and any corresponding source documents to verify the accuracy of the data.

6.0 INFORMED CONSENT

Subject consent will be obtained for all subjects willing to participate in the clinical study. No study procedures (data collection) may be done until the subject has provided a signed informed consent. The consent form will contain non-technical language describing the study procedures.

Once a potential subject has been identified for study participation (a moderate or greater infiltration has been noted), the Investigator or authorized designee will approach the subject to explain the purpose and scope of the clinical study, along with prospective risks, and benefits of participation. The subject must be given the opportunity to ask questions about the study and must be given sufficient time to decide to participate in the study or not. Any additional information requested by the prospective subject should be provided.

If the subject agrees to participate, the informed consent form must be signed and personally dated by the subject. The investigator or an authorized member of the research team who has witnessed the subject's signature must also sign and date the informed consent, prior to enrollment of the subject. A copy of the completed informed consent form must be provided to the subject. Local IRB regulations regarding obtaining informed consent must be followed. The subject's medical record should have a notation regarding the signing of the informed consent.

If a subject is unable to provide written consent due to limitations in ability to read or write, informed consent shall be obtained with the subject's LAR (legally authorized representative) and an independent witness shall be present throughout the process. The written informed consent form and any other information shall be read aloud and explained to the subject and, whenever possible, the subject shall sign and personally date the informed consent form. The witness also signs and personally dates the informed consent form attesting that the information was accurately explained, and that informed consent was freely given.

The consent form will include patient authorization to release PHI limited to that collected in the study to Lucerno Dynamics.

7.0 IRB INFORMATION

The protocol will be reviewed and approved by the site IRB prior to study initiation. Adverse events will be reported to the IRB in accordance with the standard operating procedures and policies of the IRB.

Any documents that the IRB may need to fulfill its responsibilities (such as protocol, protocol amendments, information concerning subject recruitment, payment or compensation procedures, or other pertinent information) will be submitted to the IRB. The IRB's written unconditional approval of the study protocol will be in the possession of the Study PIs before the study is initiated. The IRB's unconditional approval statement will be transmitted by the Study PIs to Lucerno prior to study initiation. This

approval must refer to the study by exact protocol title and number and should identify the documents reviewed and the date of review.

Protocol modifications or changes may not be initiated without prior written IRB approval except when necessary to eliminate immediate hazards to the subjects or when the change(s) involves only logistical or administrative aspects of the study. Such modifications will be submitted to the IRB and written verification that the modification was submitted and subsequently approved should be obtained.

The IRB must be informed of revisions to other documents originally submitted for review; new information that may affect adversely the safety of the subjects of the conduct of the study; an annual update and/or request for re-approval; and when the study has been completed.

8.0 ADDITIONAL RECORDS AND REPORTS

8.1 Data handling and record-keeping

Data will be captured using the Lara™ System, the site PET/CT scanner and a study CRF. Other than the scintillation data captured, the following information is also captured via drop down menus on the home screen at the time of data download:

Subject Height - in or cm

Subject Mass – lb. or kg

Subject Age Group: <16, 16-49, 50-69, >70

Subject Glucose:

Radiotracer:

Dose (mCi):

NM Technologist performing the injection

Flush Volume:

Injection Orientation – Unknown, Right, Left

Injection Locations – Unknown, Antecubital, Forearm, Hand, Wrist, Foot, Port, Other

Injection Technique – Unknown, Butterfly, IV, IV Drip, Straight Stick, Other

Auto Injection – Unknown, No, Yes

Needle Gauge – Unknown, 14, 16, 18, 20, 22, 23, 24, 25

At the time of data entry, the NM Technologist enters the subject's identifying hospital record number. This number is cross-referenced to a Lucerno identification number to allow the site to identify the subject and match the data with the subject. The cross reference between the hospital and Sponsor numbers is recorded at the site. Only Lucerno's identification number is transmitted, with other collected data, to the Lucerno server. The transmission is encrypted and contains no Protected Health Information.

Completed case report forms will be scanned and sent via secure e-mail to Lucerno Dynamics on a pre-determined schedule. All study documents, including paper case report forms will be kept in a secured, locked location at Wake Forest Baptist Medical Center.

8.2 Record maintenance and retention

Lucerno and the Study PIs will maintain records to include:

- IRB correspondence (including approval notifications) related to the clinical protocol including copies of adverse event reports and annual or interim reports
- Current and past versions of the IRB-approved clinical protocol and any protocol amendments
- Signed Study PIs Agreements and Certifications of Financial Interests of Clinical Investigators
- Curriculum vitae (Study PIs and any clinical protocol sub-investigators)
- Certificates of required training (e.g., human subject protections, Good Clinical Practice, etc.) for the Study PIs and key staff
- Source Documents or certified copies of Source Documents
- Monitoring visit reports
- Copies of study correspondence including any notifications of adverse effect information
- Subject screening and enrollment logs
- Subject Case Report Forms
- Signed Subject Informed Consent Forms
- Subject identification code list
- Final report

Lucerno and Study PIs will retain the specified records and reports for at least two years following completion of the study. No records will be destroyed without explicit permission from Lucerno Dynamics.

